Phase 1c: Theatre testing of BI alpha-version. We will recruit a sample of 10 MSM, using the eligibility criteria from Phase 1b, to conduct a “theatre test” of the BI. MSM who participated in earlier phases will be excluded to provide different perspectives. Participants who are seeking HIV testing at the target venues will be recruited using a screening item concerning their interest in the study that will be included on the standard post-test assessment, and their participation will be anonymous. Interested participants will simply wait in the testing room for study staff after VCT is complete. Staff will then provide them with a tablet and headphones in order to complete the full intervention. Afterward, participants will complete a brief questionnaire and interview about their perceptions of the acceptability and feasibility of delivering a BI in this environment, as well as comments they have about each BI component. Participants will receive \$30 for completing the theatre test.

Qualitative analysis. Recordings of all focus groups and interviews will be transcribed via commercially available software. Data will be analyzed using modified grounded theory methods⁹⁰, with two independent coders arriving at a consensus on major themes identified. This qualitative data will allow us to refine the assessment instruments and BI components for population sensitivity. As such, the study team will review the analysis, and assess the strengths/weaknesses of each of the components based on these findings.

C.4.2. PHASE 2: PILOT TESTING

Specific Aim 2 is to conduct a pilot randomized controlled trial of our BI, and explore preliminary evidence of its efficacy for reducing sexual risk and alcohol use among a sample of high-risk MSM seeking HIV testing in community venues. As such, we will randomize 40 MSM who receive HIV testing at the identified venues to either the standard VCT group + attention-matched control (AC), or the VCT + Intervention (BI) group. We will test the hypothesis that those in the BI group will report reductions in sex risk outcomes, sex under the influence of alcohol, and alcohol use at 1-, 3-, and 6-month follow-ups compared to the VCT+AC group.

C.4.2.1. Methods

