Randomization/Design. Participants will be randomly assigned to either the control or intervention groups by the software. Those randomized to the BI condition will complete the intervention, which will be delivered on a Windows tablet (with noise-cancelling headphones). Those randomized to the AC group (attention control) will watch a set of videos on the tablet on improving dietary and exercise habits. At the end of their session, participants in both groups will complete brief exit interviews and confirm contact information.

Follow-up Assessments. Follow-up assessments will be conducted at 1-, 3-, and 6-months following the intervention session. At each of these intervals, study staff will call participants and ask to schedule an appointment to come to the research offices. At these 45-minute appointments, participants will complete an assessment battery delivered on a tablet. Participants will receive \$50 for each assessment appointment, plus a \$50 bonus for completing all follow-up assessments.

C.4.2.2. Measures (see Appendix E)

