Baseline/Eligibility Assessments. The SDS¹⁷ will be used to assess symptoms of substance dependence for methamphetamine, cocaine, heroin/opiates, and alcohol. The SDS has demonstrated good validity and excellent reliability with respect to these drugs ($\alpha=0.80-0.85$)^{14; 15; 17}. In addition, a 30-day Timeline Follow Back (TLFB)^{18; 19}, administered online, will be used to assess alcohol use and sexual behavior during that period. The TLFB presents a calendar of each recall period, and participants respond by clicking on a box that represents a given day, answering several questions about that day. Questions will assess the number of standard drinks consumed on that day, the number of hours over which these drinks were consumed, the total number of sex partners, their relationship with each (e.g., steady vs. casual), the HIV status of each (e.g., HIV+, HIV-, or unknown), whether they asked about their partner’s HIV/STI status or the last time they were tested, sex acts performed with each, condom use for each act, and whether sexual activity took place while under the influence of alcohol. Meta-analyses have shown that TLFBs for assessing alcohol use and sex behavior are reliable when administered electronically and online²⁰. Other studies explicitly comparing online vs. in-person TLFBs for sexual behavior²¹, and comparing the TLFB to biological measures for alcohol use²² have confirmed the validity of online TLFBs. TLFB data will be used to determine participants’ drinking eligibility, while single items will assess all other eligibility criteria. Finally, stages of change will be assessed using the Stages of Change (Short Form)²³ and a 4-item stages of change measure for HIV-risk²⁴⁻²⁶.

Efficacy outcomes. Our primary outcomes will be the number of unprotected anal sex events, number of sex events under the influence of alcohol, frequency of drinking, and the

number of heavy drinking days over the past month. Outcomes will be assessed via 30-day Timeline Follow Back (TLFB)^{91, 93} at each follow-up.

Secondary outcomes. We will also assess whether participants talked to their partners about their HIV/STI status and recent testing, and whether during each follow-up window, participants engaged in self-initiated HIV testing, sought STI screening, or sought information about pre-exposure prophylaxis. Change motivation and stages will also be explored as secondary outcomes.

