Primary analyses. Our hypotheses related to Specific Aim 2 are that participants in the intervention group will report (1) fewer unprotected anal sex events, (2) fewer events involving sex while under the influence of alcohol, and (3) lower frequency of drinking and a reduced number of heavy drinking days versus the control group. These hypotheses will be evaluated using an intention-to-treat comparison of the rates of our primary outcomes at 1-, 3-, and 6-month follow-ups, using an incidence rate ratio (IRR) and 95% CI. Given the count nature of the data, we will use a Poisson regression covarying for key baseline covariates, and compare IRRs across the two treatment conditions at each time point. As conclusions about statistical significance will be limited due to the small sample, clinically meaningful differences in the pattern of IRRs and means (for alcohol use variables) across groups will be used to evaluate our hypotheses. However, if available data produce stable results, generalized estimating equations (GEEs) using binomial distributions and logit-link functions will also be used to explore differences in these outcomes across time and treatment condition. We will also explore the potential influence of the intervention on secondary outcomes and exploratory mediators. IRRs and descriptive data will be used to compare the groups in terms of their frequency of talking to partners about their status, whether they sought additional HIV testing, STI screening or information about PrEP. Descriptive mean comparisons and linear regressions controlling for baseline values will be used to compare whether HIV knowledge and perceived risk, peer safe sex norms, and safe sex behavioral skills differ across the groups.

C.4.3. Recruitment

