Exclusion criteria:

4. Individuals who are HIV-positive
5. Individuals who participated in other phases of the research
6. Individuals who report being coerced to participate

Types of Data. This study will involve collecting four types of data:

1. Focus groups (N = 24) in Phase 1-a, generating written notes, digital recordings, and transcripts.
2. Qualitative process interviews for both individual interviews (Phase 1-b, N = 35), generating written notes, digital recordings, and transcripts, written, open-ended questionnaire data.
3. Quantitative data on clinical outcomes for the pilot sample (Phase 2, N = 40), obtained via electronically-administered questionnaires.

All study procedures, including data collection, will be conducted by either the Contact PI/Project Director ([name]), Co-PIs (Drs. [name] and [name]) or a Research Assistant. Research Assistants will receive intensive training in all study procedures from [name] and other PIs. Procedures for assigning individual participants to trial arms in Phase 2 will be based on a computer-generated randomization sequence that is completed automatically by the software. A randomized design is appropriate for our goal of pilot testing a behavioral intervention.

C.4.4.1. Sources of Materials

In Phase 1a, we will collect data directly from informants using focus group methodology. These methods will produce qualitative data in the form of digital recordings (which will be recorded using a digital voice recorder [DVR]) and transcripts for analysis. Focus groups will be moderated by [name] and will generate data in the form of written notes, which will contain no individual participant identifiers. We will use the Phase 1a data to adapt

intervention protocols for use with the target populations and settings.

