## **STATISTICAL ANALYSIS PLAN**

**Title:** Brief Electronic Intervention for Heavy Drinking and Sex Risk Among Men who have sex with Men  
Seeking HIV Testing

**NCT#:** NCT03435783

**Date of document:** Last reviewed and approved by Brown IRB on 7/21/17

**Statistical analysis plan.** We hypothesized that participants using the web-based intervention would report (1) fewer new anal sex partners, (2) fewer condomless anal sex events, and (3) lower frequency of drinking, (4) lower frequency of binge drinking, and (5) a lower average number of drinks per drinking day versus the control group. These hypotheses will be evaluated using an intention-to-treat comparison of the rates of our primary outcomes at 1-, 2-, and 3-month follow-ups, using incidence rate ratios (IRRs) and 95% CI. Given the count nature of much of the data, we will use a Poisson regression covarying for key baseline covariates, and compare IRRs across the two treatment conditions at each time point. As conclusions about statistical significance will be limited due to the small sample, clinically meaningful differences in the pattern of IRRs and means (for alcohol use variables) across groups will be used to evaluate our hypotheses. However, if available data produce stable results, generalized estimating equations (GEEs) using binomial distributions and logit-link functions will also be used to explore differences in these outcomes across time and treatment condition. We will also explore the potential influence of the intervention on secondary outcomes and exploratory mediators. IRRs and descriptive data will be used to compare the groups in terms of their frequency of talking to partners about their status, whether they sought additional HIV testing, STI screening or information about PrEP. Descriptive mean comparisons and linear regressions controlling for baseline values will be used to compare whether HIV knowledge and perceived risk, peer safe sex norms, and safe sex behavioral skills differ across the groups.

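### The alcohol hypotheses rest partly on group means with no stated baseline adjustment or interval, and the Poisson covariates are not said to include the outcome's own baseline value

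*SAP*

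**What the plan says.** The SAP lists five hypotheses, three of them on alcohol: frequency of drinking, frequency of binge drinking, and average drinks per drinking day. All five are to be evaluated by intention to treat with IRRs and 95% CIs. The model is the one in the protocol (C.4.2.2, Data Analysis Plan, Primary analyses): "we will use a Poisson regression covarying for key baseline covariates". Neither document lists those covariates. The SAP justifies the count model by the nature of much of the data, not all of it.

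Both documents then concede that the small sample limits conclusions about significance, and say that "clinically meaningful differences in the pattern of IRRs and means (for alcohol use variables) across groups will be used to evaluate our hypotheses". They do not say whether these means are adjusted, give them no interval, and set no size for a meaningful difference.

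For the exploratory mediators the same SAP paragraph is more specific: "linear regressions controlling for baseline values will be used to compare whether HIV knowledge and perceived risk", and likewise norms and behavioral skills, alongside descriptive comparisons of means.

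The baseline data exist. Under Measures (Protocol C.4.2.2), the 30-day TLFB at baseline "will be used to assess alcohol use and sexual behavior during that period", and a 30-day TLFB is used again at each follow-up.

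On design, "we will randomize 40 MSM who receive HIV testing at the identified venues" (Protocol C.4.2). Allocation uses a "computer-generated randomization sequence that is completed automatically by the software" (Protocol C.4.4). No ratio, blocking or stratification is described.

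**The concern.** How much a man drinks in one month usually says something about how much he drinks a few months later. With about 20 men per arm and no described stratification on drinking, the arms can differ at baseline by chance. Part of that difference persists into the follow-up means. If those means help decide the alcohol hypotheses unadjusted, the imbalance can look like an intervention effect or hide one.

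The plan has the data to limit this, and it writes out the remedy for the mediators. For the primary alcohol outcomes it leaves the analyst free to adjust for the outcome's own baseline value or not, both in the means and in the Poisson model. An adjusted IRR does not protect a conclusion drawn from unadjusted means placed beside it. The protocol (C.1, Aim 2) says that initial evidence of efficacy would lay the ground for a full-scale trial, so a false signal in either direction has a cost.

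**Working it through.** **Which alcohol outcomes have a stated model?** Drinking days and binge days in a 30-day window are counts, so the Poisson model covers them, with unlisted baseline covariates; their means also enter the judgement. Average drinks per drinking day is not a count. The SAP's count rationale does not clearly reach it, and the optional GEE is binomial with a logit link, which does not suit an average. No model in the plan is clearly assigned to it, so it may be judged on means alone. Its baseline value is defined for every participant: drinking eligibility is determined from the TLFB and requires recent heavy drinking, so each man has at least one drinking day at baseline.

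**Inputs.** The documents give no power calculation, SD, correlation or dropout rate, so there is no plan figure to reproduce.
- Total N = 40 (Protocol C.4.2; the SAP gives none).
- n = 20 per arm, assuming 1:1 allocation.
- Baseline-to-follow-up correlation r = 0.3, 0.5 and 0.7 (assumed).
- Equal SDs and a normal approximation (assumed).
- Cut-offs of 0.3 and 0.5 SD, for illustration only.

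**Step 1: unadjusted means, no true effect.** SE of the difference = sqrt(1/20 + 1/20) = 0.316 SD.
- P(|difference| > 0.3) = 2[1 − Φ(0.3/0.316)] = 34.3%.
- P(|difference| > 0.5) = 2[1 − Φ(0.5/0.316)] = 11.4%.

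**Step 2: the part carried over from baseline.** The baseline difference has the same SE, 0.316 SD, so its 95% chance range is ±1.96 × 0.316 = ±0.62 SD. A baseline imbalance of one SE shifts the expected follow-up difference by r × 0.316, which is 0.09, 0.16 or 0.22 SD for r = 0.3, 0.5 or 0.7. As a share of the chance variance in Step 1 this is r², or 9%, 25% or 49%. The 34% in Step 1 is total chance variation, and only this share of its variance comes from baseline.

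**Step 3: baseline-adjusted difference.** SE = sqrt(2/n) × sqrt(1 − r²) × sqrt(1 + 1/(2n − 4)). The last factor is the small-sample cost of estimating the slope.

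| Analysis | SE (SD units) | P(above 0.3 SD) | P(above 0.5 SD) |
|---|---|---|---|
| Unadjusted | 0.316 | 34.3% | 11.4% |
| Adjusted, r = 0.3 | 0.306 | 32.7% | 10.2% |
| Adjusted, r = 0.5 | 0.278 | 28.0% | 7.2% |
| Adjusted, r = 0.7 | 0.229 | 19.0% | 2.9% |

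**Step 4: sensitivity to loss.** With an assumed 20% dropout (20 × 0.8 = 16 per arm), the unadjusted SE is sqrt(2/16) = 0.354 SD. The chance of a null difference above 0.3 SD is 39.6% unadjusted, against 38.2%, 33.6% and 24.3% adjusted at r = 0.3, 0.5 and 0.7.

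**The case against.** A reader might infer that the alcohol hypotheses will be judged on raw means, and that the primary outcomes receive less adjustment than the mediators. The documents do not support either statement. They call the means neither raw nor adjusted. The IRRs stand beside the means in the same sentence, and the preceding sentence plans a Poisson model with baseline covariates and 95% CIs for the hypotheses, alcohol included. On a plain reading at least two of the three alcohol hypotheses get a regression and an interval. The mediators, for their part, also get descriptive mean comparisons. The supportable contrast is narrower: control for baseline values is explicit for the mediators, while for the primary outcomes the covariates are unnamed.

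The size is also open to challenge. The range of r is assumed. Selecting men on recent heavy drinking may lower r, and at r = 0.3 the gain nearly vanishes. The 1:1 ratio and the 0.3 SD cut-off are not in the documents. Finally, this is a pilot, and the plan itself says that significance conclusions will be limited.

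All of this stands as a limit on the claim. What it does not answer is that the plan permits unadjusted means to help decide primary hypotheses, and that one alcohol outcome has no clearly assigned model. The small-sample caveat adds to the exposure, because it shifts weight from significance to the pattern of IRRs and means.

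**Conclusion.** The point holds in limited form. The alcohol hypotheses are evaluated partly on group means for which neither baseline adjustment nor an interval is stated, and the Poisson model is not said to include the outcome's own baseline value. The exposure is greatest for average drinks per drinking day.

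At 20 per arm, adjustment lowers the chance of a null difference above 0.3 SD from 34% to about 33%, 28% or 19% at r = 0.3, 0.5 or 0.7. The benefit is small if r is low and worthwhile if it is moderate or high. Even at r = 0.7, roughly one null comparison in five exceeds 0.3 SD, so adjustment does not make differences of that size reliable evidence. These figures rest on 1:1 allocation, equal SDs, a normal approximation and the assumed r.

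**What to change.** Amend the SAP paragraph as follows.

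- In every primary Poisson model, name the outcome's own baseline TLFB value as a prespecified covariate, and list any others. For count outcomes, state that this adjusted IRR with its 95% CI is the deciding estimate.
- For average drinks per drinking day, use the baseline-adjusted mean difference with its 95% CI, from a linear regression on arm and the baseline value. State how follow-up windows without a drinking day are handled, since the average is undefined there.
- Report unadjusted means by arm as description only.
- State in advance what size of IRR or mean difference counts as clinically meaningful, since adjustment alone leaves that judgement open.

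The cost is SAP wording and one estimated coefficient per model. No new data are needed, because the baseline TLFB is already collected. At r near zero the small-sample term would make the adjusted SE slightly larger than the unadjusted one (0.321 against 0.316 SD), a negligible loss.

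### The exploratory GEE across follow-ups is binomial/logit for every primary outcome, with no denominator or cut-point; the family suits the drinking-day outcomes once a denominator is written, but not the event counts or drinks per drinking day

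*SAP*

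**What the plan says.** The SAP lists five hypotheses. Two are event or partner counts ("fewer new anal sex partners, (2) fewer condomless anal sex events"), two are drinking and binge-drinking frequency, and the fifth is "a lower average number of drinks per drinking day versus the control group". The protocol (C.4.2.2 Measures, Efficacy outcomes) defines its own set: "Our primary outcomes will be the number of unprotected anal sex events, number of sex events under the influence of alcohol, frequency of drinking". It completes that list with heavy drinking and fixes the recall window: "number of heavy drinking days over the past month. Outcomes will be assessed via 30-day Timeline Follow Back".

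The main analysis is a Poisson regression giving an incidence rate ratio (IRR) at each follow-up separately. The protocol (C.4.2.2 Data Analysis Plan, Primary analyses) justifies it thus: "Given the count nature of the data, we will use a Poisson regression covarying for key baseline covariates". The SAP is more guarded and says only that much of the data are counts. Both documents then make a further analysis, over time and by arm, conditional on stable results. The SAP puts it this way: "generalized estimating equations (GEEs) using binomial distributions and logit-link functions will also be used to explore differences in these outcomes across time". The protocol has the same words: "generalized estimating equations (GEEs) using binomial distributions and logit-link functions will also be used to explore differences in these outcomes".

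Neither document states a number of trials, a threshold for a yes/no recode, or a different family for any outcome.

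**The concern.** A binomial model with a logit link needs either a yes/no response or a number of events out of a known number of trials. Partner counts and sex-event counts have no stated upper limit, and mean drinks per drinking day is neither a count out of trials nor a proportion. Taken at its word, the sentence assigns these outcomes a family that does not fit them. If the authors had a recode or a denominator in mind, the text does not say which, and the choice changes what is estimated.

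At stake is the one analysis that pools the three follow-ups and looks at change over time by arm. With 40 participants, the pooled analysis is where repeated measurements could add something to the visit-by-visit ratios. As written, its family, denominator or cut-point could be chosen after the data are seen.

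**Working it through.** The documents give no event rates, dispersion, allocation ratio or power figure, so there is no figure of the plan's to reproduce. All rates below are assumptions, and 20 per arm is an assumed equal split of the stated 40. As a reference point, the eligibility minimum of one unprotected event in three months is about 0.33 per month.

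**1. Raw counts in a logit model (worst-case reading).** For each arm the estimating equation sets the fitted probability equal to the mean count m. The estimated odds ratio (OR) is therefore [m1/(1 − m1)] / [m0/(1 − m0)], with m1 = IRR × m0. Example with m0 = 0.5 and IRR 0.5: (0.25/0.75)/(0.5/0.5) = 0.33.

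| Control mean per 30 days | OR if IRR = 0.5 | OR if IRR = 0.7 |
|---|---|---|
| 0.33 | 0.40 | 0.61 |
| 0.5 | 0.33 | 0.54 |
| 0.75 | 0.20 | 0.37 |
| 0.9 | 0.09 | 0.19 |

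Once an arm mean reaches 1 there is no finite solution.

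Simulated trials agree (20 per arm, three visits, IRR 0.5, overdispersed counts with variance-to-mean ratio 1.5 to 3, no dropout, 300 trials per setting). At control means of 0.33, 0.5, 0.75, 1, 2 and 4 the fit converged in 99.7%, 100%, 88%, 48%, 0% and 0%. The median OR among converged fits at the first four was 0.36, 0.30, 0.25 and 0.16. A log-link count GEE on the same data converged in at least 99.7%, with median IRR 0.46 to 0.52.

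**2. Yes/no recode (more natural reading).** On similar simulated data, any-versus-none fitted in 96 to 100% of trials, with median OR about 0.47 to 0.49 at control means up to 1. So it neither fails nor inflates the effect there. Two costs remain.

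- *The cut-point sets the answer.* Take a negative binomial with dispersion k = 1, so P(Y ≥ c) = [μ/(1 + μ)]^c, and hold the IRR at 0.6. With control mean 1 (treated mean 0.6), the OR is 0.60, 0.49 and 0.23 for cut-points of 1, 2 and 5 events. With control mean 3 it is 0.60, 0.55 and 0.40. The match of OR and IRR at a cut-point of 1 is a property of k = 1, where the odds of any event equal the mean.
- *Information is lost.* In gamma-Poisson simulations (20 per arm, three visits, 600 trials per setting), the log-link count GEE against any-versus-none reached significance in 40% against 17% (mean 3, IRR 0.6, k = 1), 58% against 30% (mean 3, IRR 0.5, k = 1), 76% against 42% (mean 3, IRR 0.5, k = 2) and 85% against 29% (mean 6, IRR 0.5, k = 2). Standard errors were uncorrected for small samples, so the levels are optimistic; the contrast is what matters.

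**3. Drinks per drinking day.** If drinks are recorded as whole numbers, each drinking day has at least one, so the mean is at least 1 and the raw logit fit has no finite solution. None of 450 simulated fits converged (control means 3, 5 and 7); a Gaussian GEE converged in all 450.

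**4. Drinking days and binge or heavy drinking days.** The 30-day Timeline Follow-Back supplies a natural denominator. Ten against six days out of 30 (rate ratio 0.6) gives (0.2/0.8)/(0.333/0.667) = 0.50, a proper odds ratio. Simulated fits of days out of 30 converged in 450 of 450 (control means 4.5, 9 and 15); raw day counts in 0 of 450.

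**5. Condomless acts as a share of all acts.** The calendar also records "sex acts performed with each, condom use for each act, and whether sexual activity took place while under the influence of alcohol" (protocol, Baseline/Eligibility Assessments), so a denominator could be built. The estimand changes, though. If men halve their acts with unchanged condom use, condomless events halve but the OR is 1.00. If acts are unchanged and the condomless share p0 halves, OR = [0.5p0/(1 − 0.5p0)]/[p0/(1 − p0)], which is 0.41, 0.29 and 0.17 at p0 of 30%, 60% and 80%.

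**The case against.** The strongest reply is that nobody would feed counts of 3 or 5 into a Bernoulli likelihood. Binomial/logit points to a yes/no recode or days out of 30, and on those readings the model fits. This stands: the distortion and non-convergence in step 1 are a worst case, seen in one software package. Other packages may reject such data outright, and counts above 1 would be visible to the analyst. A reader might infer that the GEE will fail or exaggerate the effect. The documents do not support that, because they do not say that raw counts will be used.

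Part of the step 1 gap is also the ordinary difference between an odds ratio and a rate ratio: 0.35 against 0.5 gives 0.54 whether it is a mean count or 15 days out of 30 reduced by 30%. The distinction is that days out of 30 are a real proportion, whereas a mean count is not a probability.

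The analysis is also exploratory and conditional, and the hypotheses are to be judged on the pattern of rate ratios and means. This limits the stakes but does not mend the sentence. The stability condition would screen out a fit that fails, but not a yes/no fit that runs with a cut-point chosen afterwards. Reading binomial as a slip for negative binomial does not help either, since a logit link does not suit a count mean. No single reading covers all five SAP outcomes.

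**Conclusion.** The point holds in a limited form. The stated family does not suit new partners (SAP), condomless or unprotected anal sex events (both documents), alcohol-involved sex events (protocol only) or drinks per drinking day (SAP only). It is sound for drinking days and binge or heavy drinking days once the 30-day denominator is written. On the likely yes/no reading, the cost is lost information, an odds ratio that moves with the cut-point (0.60 to 0.23 at a fixed IRR of 0.6 and control mean 1), and a result that no longer matches the hypothesis of fewer events or the per-visit IRRs.

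Two wider inferences should be resisted. The main analysis is not undermined: the per-visit Poisson ratios do not depend on the GEE. Nor do both documents call every outcome a count; the SAP's wording leaves room for drinks per drinking day to be something else.

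The specification gap itself rests on the text. The sizes rest on assumed rates, dispersion and equal allocation. It is worth fixing before the data are examined, at modest priority.

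**What to change.** Replace the GEE sentence with one family and link per outcome:

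- **New partners and condomless anal sex events** (and, in the protocol, alcohol-involved sex events): log link, Poisson variance, robust standard errors, reporting IRRs.
- **Drinking days and binge or heavy drinking days:** binomial/logit on days out of the 30-day window, robust standard errors, reporting odds ratios.
- **Drinks per drinking day:** Gaussian GEE with identity link, reporting mean differences.
- **Binomial/logit otherwise** only for yes/no outcomes stated in advance. If condomless acts as a share of all anal acts is wanted, list it as a separate outcome with its denominator.

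The same sentence could name the working correlation and a small-sample correction to the robust standard errors, given about 40 clusters. The cost is SAP and protocol wording and slightly more analysis code, with results on three scales instead of one. No new data are needed: the calendar already records daily drinks, partners, acts and condom use.

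### Three yes/no service-seeking outcomes are to be compared by incidence rate ratios; if the plan's Poisson model is carried over with its default variance, their intervals will be too wide

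*SAP*

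**What the plan says.** The protocol (C.4.2.2 Measures, Secondary outcomes) defines the three items as "whether during each follow-up window, participants engaged in self-initiated HIV testing, sought STI screening, or sought information about pre-exposure prophylaxis". Each man therefore contributes a 0 or a 1 per item and window.

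The SAP, and in the same words the protocol's Data Analysis Plan (Primary analyses), begins the relevant sentence "IRRs and descriptive data will be used to compare the groups in terms of their frequency of talking to partners about their status" and ends it with "whether they sought additional HIV testing, STI screening or information about PrEP". The sentence names no model, variance estimator or interval. The role of these outcomes is exploratory: "We will also explore the potential influence of the intervention on secondary outcomes and exploratory mediators".

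The model has to be looked for earlier in the same paragraph, where the primary outcomes are handled: "Given the count nature of much of the data, we will use a Poisson regression covarying for key baseline covariates", with results given "using incidence rate ratios (IRRs) and 95% CI". The one binomial model in the plan is conditional on stable results: "generalized estimating equations (GEEs) using binomial distributions and logit-link functions will also be used to explore differences in these outcomes". In context, the outcomes meant there are the primary ones.

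**The concern.** An incidence rate ratio compares event counts per unit of time. Whether a man sought a service in a window is not a count, so the ratio of the two arms' proportions is a risk ratio.

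Poisson regression still estimates that ratio correctly. Its default standard error, however, takes the variance of each man's response to equal its mean, p. A 0/1 response has variance p(1-p), which is smaller. An analyst who follows the paragraph as written, with standard software settings, would report intervals wider than the data warrant.

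With about 20 men per arm, precision is already poor. The plan also says that effects will be judged by the pattern of IRRs and means more than by significance. The interval is what shows a reader how much weight such a pattern can bear.

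**Working it through.** The documents give no interval, power figure or uptake rate for these outcomes, so there is no figure of the plan's own to reproduce.

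**Inputs**
- Total sample: "we will randomize 40 MSM who receive HIV testing at the identified venues" (protocol C.4.2).
- Allocation: not stated. Assumed 1:1, so n = 20 per arm. With 16 per arm (20% loss) the standard-error ratios below are the same.
- Uptake p of each service: not stated. Assumed range 10% to 70%.
- Interval level: 95%, stated for the primary outcomes and assumed to carry over.

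**Formulas**, with a and b the numbers answering yes in the two arms:
- Poisson, model-based: SE of log ratio = sqrt(1/a + 1/b)
- Binomial: SE of log risk ratio = sqrt(1/a - 1/n + 1/b - 1/n)
- With the same p in both arms, the first divided by the second is 1/sqrt(1-p).

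**Excess in the standard error, equal uptake**

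| p | 1/sqrt(1-p) | Excess |
|---|---|---|
| 0.1 | 1.05 | 5% |
| 0.2 | 1.12 | 12% |
| 0.3 | 1.20 | 20% |
| 0.5 | 1.41 | 41% |
| 0.7 | 1.83 | 83% |

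With unequal uptake the ratio is 1.17 for 40% versus 20%, and 1.22 for 50% versus 25%.

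**Worked example, 10/20 versus 6/20 (assumed).** The ratio is 0.50/0.30 = 1.67.
- Poisson: SE = sqrt(1/10 + 1/6) = 0.516, 95% CI 0.61 to 4.59.
- Binomial: SE = sqrt(1/10 - 1/20 + 1/6 - 1/20) = 0.408, 95% CI 0.75 to 3.71.
- The standard error is 0.516/0.408 = 1.26 times as large. Both intervals include 1.

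**A case where the reading changes, 14/20 versus 6/20 (assumed).** The ratio is 2.33.
- Poisson: SE = sqrt(1/14 + 1/6) = 0.488, 95% CI 0.90 to 6.07.
- Binomial: SE = sqrt(1/14 + 1/6 - 2/20) = 0.372, 95% CI 1.13 to 4.83.

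**Check by fitting the model.** For 10/20 versus 5/20, a Poisson GLM gives SE 0.548 with default variance and 0.447 with robust variance. The intervals for the ratio of 2.0 are 0.68 to 5.85 and 0.83 to 4.81. The point estimate is the same.

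**Exact coverage of nominal 95% intervals** (equal uptake, at least one yes in each arm)

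| n per arm | p | Poisson SE | Binomial SE |
|---|---|---|---|
| 20 | 0.2 | 99.5% | 99.2% |
| 20 | 0.3 | 99.1% | 97.7% |
| 20 | 0.5 | 99.5% | 96.1% |
| 200 | 0.3 | 98.1% | 95.2% |
| 200 | 0.5 | 99.5% | 94.9% |

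The over-coverage of the Poisson interval persists at 200 per arm, so it comes from the variance assumption and not from the small sample. At 20 per arm and uptake of 20% or less, the two intervals behave almost alike and both are conservative. At 10% uptake a ratio cannot be formed in 1 - (1 - 0.9^20)^2, or about 23%, of trials, because one arm has no yes. That favours a risk difference when uptake is low.

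**The case against.** The strongest reply is that the documents do not commit to the faulty calculation. The 95% interval and the Poisson model are both stated for the primary outcomes. The secondary sentence promises only IRRs and descriptive data, and no variance estimator is named anywhere. The sentence can also be read as giving IRRs to the frequency of talking to partners and descriptive data to the three yes/no items.

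This stands in part. A reader might infer that the plan's intervals for these outcomes are definitely too wide. The text supports only the conditional statement: they will be if the named model is used with its default variance. The reply does not remove the point. Poisson regression is the only route to an IRR that the plan offers, and it is justified there by count data, which these items are not. On the alternative reading the yes/no items have no effect measure at all, and the same sentence is needed to supply one.

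A reader might also infer that the plan has its methods swapped, with binomial models for counts and Poisson for binary items. It does not: the count outcomes get Poisson regression first, and the binomial GEE is additional and conditional.

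Nor do the documents say that service uptake will drive the design of the next trial. Specific Aim 2 says only that the quantitative and qualitative data will inform any changes needed before a larger trial.

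Finally, the error is conservative, is only about 5% at 10% uptake, and concerns outcomes labelled exploratory in a plan that already warns about significance. All of that is correct and limits the weight of the point.

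**Conclusion.** The point holds in conditional form. An incidence rate ratio with default Poisson error does not suit a 0/1 outcome. If used here, it leaves the unadjusted ratio intact but mislabels it, and it inflates the standard error by about 5% to 41% for uptake between 10% and 50%. It cannot manufacture a positive finding; it can obscure a difference.

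The size rests on assumed uptake, on 1:1 allocation, and on the Poisson model, its model-based variance and the 95% level being carried over from the primary analysis. The consequence is modest in an exploratory comparison of 40 men. The correction is nearly free, so it is worth making.

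**What to change.** Add one sentence to the SAP and align the protocol's Data Analysis Plan with it. For self-initiated HIV testing, STI screening and seeking PrEP information, at each follow-up, do one of the following:

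- report a risk ratio with 95% CI from Poisson regression with robust (sandwich) variance and a small-sample correction; or
- report a risk difference with a Newcombe or exact interval, which remains usable when one arm has no yes answers.

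State which of the two is the main summary, call it a risk ratio or risk difference, and keep the term IRR for the count outcomes. No new data, visits or participants are needed.
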